Session I of an intravenous fentanyl citrate administration, with at least a one week washout interval between Study Sessions.

The study products are:

- Single intravenous (100 µg) administration of fentanyl citrate (50 µg/mL)
- Duragesic® TDDS containing fentanyl (25 µg/h) to be worn for 3 days (72h)
- Mylan fentanyl TDDS (Generic) containing fentanyl (25 µg/h) to be worn for 3 days (72h)

Each Subject will be his/her own control.

Administration of naloxone injection will be used to test for withdrawal prior to using any study products, and to be used emergently in case of fentanyl toxicity. Naltrexone oral tablets will be used to block the opioid receptors to avoid any clinical effects or side-effects of fentanyl.

Blood samples will be obtained as follows (based on administration route):

- 60 min pre-IV administration and then up to 36 hr (1.5 days) post start of IV administration
- 60 min pre-application and then up to 192 hr (8 days), during 3 day wear and post removal of RLD
- 60 min pre-application and then up to 192 hr (8 days), during 3 day wear and post removal of Generic product

B) Residual Drug Analysis determination of Strength

In conjunction with the above described study residual drug analysis will also be conducted for the used RLD and Generic TDDS described in Part A.

- Prior to administration to the Subject as described in Part A, the TDDS will be weighed and the weight recorded.
- The pouch, release liner and all items coming into contact with the TDDS (gloves, forceps, etc.) to be applied in Part A will be retained for analysis.
- The used TDDS will be retained for drug content analysis.
- Upon removal of the product after prescribed wear Session, the skin (at site of application) will be swabbed and the swab retained for drug content analysis.
- All items coming into contact with the TDDS during removal from the Subject and storage in a separate labeled sealable foil pouch for analytical retention will be analyzed for drug content.

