3 OBJECTIVES

3.1 Study Objectives

The objectives of this open label, randomized, crossover study are to

- To explore bioequivalence of Duragesic® transdermal system and generic Mylan fentanyl TDDS, and compare bioavailability to direct IV infusion of fentanyl citrate.
- To conduct release rate analysis of generic fentanyl (Mylan) TDDS compared to Duragesic® TDDS.
- To determine the residual drug content of the Duragesic® and generic fentanyl TDDS.

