4 STUDY DESIGN

This is a three treatment open-label, randomized cross-over clinical study with a Run-In Study Session I of intravenous fentanyl citrate, followed by randomization to Duragesic® and generic fentanyl in a sequential, 2-Session fashion with at least a one week wash-out Session between the sessions.

The study design is shown below:

Study Session I (Run-in)	Randomization		Study Session II	Study Session III
Intravenous -Fentanyl		Study Arm 1	Duragesic®	Mylan Fentanyl
		Study Arm 2	Mylan Fentanyl	Duragesic®

The study will consist of a total of twenty-five Study Days (24 Subjects) within three Study Sessions, with at least a one week washout Session between successive Study Sessions. The half-life of fentanyl is approximately 24 hours. Hence, 5 days (i.e. 5 half-lives) will be sufficient for >95% of fentanyl to be eliminated from the body. Each of the 24 Subjects will be enrolled to complete all twenty-five study days (Run-In Study Session I = 5 Study Days; Study Sessions II and III = 10 Study Days each). The study is open label and not blinded, because PK assessment is not subject to participant and/or observer bias. After each Study Session is completed, the available safety data will be reviewed by an Independent Safety Monitor (ISM) to determine whether or not to proceed to the next Study Session.

Considering the objective of the study to explore bioequivalence of Duragesic® and generic fentanyl and to conduct release rate analysis of generic fentanyl to Duragesic®, the above study design would adequately address both questions. The randomization to sequences [Reference (R) –Test (T), T-R] would appropriately take into account the sequence and the Session effect for bioequivalence evaluations. Having all Subjects enter the intravenous Run-In Study Session I initially would also help in accurate determination of absolute bioavailability for Duragesic® and generic Mylan fentanyl in this study.

Each Subject will be his/her own control and each Subject will sign an institutional review board-approved consent form explaining the purpose, nature, risks, benefits, and duration of the study. The study will be conducted in accordance with good clinical practice guidelines and with the ethical principles originating in the Declaration of Helsinki.

The three Study Sessions are as follows:

Study Session I (Run-in):

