8 PHARMACOKINETICS AND STATISTICAL CONSIDERATIONS

8.1 Study Hypotheses

Given the fact that there are formulation differences between Duragesic® and Mylan fentanyl TDDS, we hypothesize that:

- a. Bioequivalence exploration.
- b. Release rate analysis.

These hypotheses will be tested by comparing the residual drug amounts in Duragesic® and Mylan fentanyl TDDS and by assessing the pharmacokinetic parameters following their application, and comparing them to the pharmacokinetic parameters estimated after direct IV infusion of fentanyl citrate.

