8.2 Pharmacokinetics (PK) Analyses

8.2.1 Pharmacokinetic endpoints

- Area under the time curve from dosing time to last measurement time (AUC_{0-t}) and peak drug activity (C_{max}) for Duragesic® TDDS and Mylan fentanyl TDDS will be used as the primary endpoint. For intravenous fentanyl, $AUC_{0-\infty}$ will be determined.
- The time to maximum concentrations (T_{max}) and $AUC_{0-\infty}$ for fentanyl from Duragesic® TDDS and Mylan fentanyl TDDS will also be determined.

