8.3 Final Analysis Plan

The primary statistical analysis will be performed on the natural log transformed AUC_{0-t} , AUC_{0-A} and C_{max} of Fentanyl from the three Study Sessions using SAS V 9.3. A linear mixed effects model will be used to assess the effects of treatment, Session, sequence and Subject within sequence on natural log transformed AUC_{0-t} , AUC_{0-C} and C_{max} . The treatment, Session, sequence effect will be treated as fixed effects and assessed at a significance level of 0.05. The Subject within sequence will be treated as a random effect. Intra and inter individual variabilities will be obtained. The least square mean estimates for the adjusted differences between treatment means (the log transformed AUC_{0-t} , AUC_{0-C} and C_{max}) and the standard error associated with these differences will be obtained. The geometric means for AUC_{0-a} will be obtained by exponentiating the log transformed AUC_{0-i} for all the three treatments to determine the absolute bioavailability.

The absolute bioavailability for Duragesic® TDDS and Mylan fentanyl TDDS will be calculated.

The analyses for IV administration of fentanyl citrate will be as follows:

Non compartmental and compartmental analyses will be conducted to estimate the PK parameters such as clearance, volume of distribution, elimination rate constant, maximum serum concentration; time of maximum serum concentration and area under the serum concentration-time curve. All analyses will be conducted using Phoenix® WinNonlin® 6.3 (Pharsight, a Certara Company, CA). Absolute bioavailability will be calculated.

The analyses for both TDDS applications (Duragesic® and Mylan fentanyl) will be as follows:

The serum fentanyl concentrations will be determined and the PK parameters such as C_{max} , T_{max} , AUC, steady concentrations (C_{ss}) of fentanyl in each Subject will be elucidated. The rate of fentanyl absorption in each Subject is calculated by dividing the C_{ss} by the clearance predicted from the IV bolus data.

Cumulative amount of fentanyl released by Duragesic® at the end of study Session will be obtained by subtracting residual fentanyl still remaining in the TDDS at the end of the study Session from the total amount of the drug present in an unused TDDS.

Similarly, cumulative amount of the drug released by the Mylan TDDS at the end of study Session is computed.

The rate of drug release from Duragesic® and Mylan TDDS will be determined.

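### The only inference planned for the exploratory bioequivalence comparison of the two patches is a 0.05 difference test; no Mylan/Duragesic ratio with a confidence interval is stated

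*Combined protocol and SAP*

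**What the plan says.** Section 3.1 opens its list of objectives with "To explore bioequivalence of Duragesic® transdermal system and generic Mylan fentanyl TDDS". Section 8.1 lists "a. Bioequivalence exploration" among the hypotheses to be tested. Section 4 defends the two randomised sequences on the ground that they "would appropriately take into account the sequence and the Session effect for bioequivalence evaluations". Section 8.2.1 states that AUC0-t and Cmax for the two patches "will be used as the primary endpoint".

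Section 8.3 then plans a linear mixed model on log-transformed AUC and Cmax "of Fentanyl from the three Study Sessions using SAS V 9.3". On inference it says: "The treatment, Session, sequence effect will be treated as fixed effects and assessed at a significance level of 0.05". It adds that adjusted differences between treatment means will be estimated on the log scale, "and the standard error associated with these differences will be obtained".

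Three things in section 8.3 come close to what is missing but do not supply it:

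- The only stated back-transformation is of AUC geometric means, and its purpose is absolute bioavailability.
- The only confidence intervals are 95% intervals for release rates.
- The two-tailed t-test at the end also concerns release rates and is also a difference test.

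**The concern.** Bioequivalence asks whether the ratio of the two patches is close enough to 1. A test at 0.05 with a null of equality asks whether the data can exclude a ratio of exactly 1. A non-significant result may only reflect imprecision, and a significant one may reflect a small difference measured precisely. What serves the objective is the estimated ratio with its interval, and section 8.3 does not ask for it.

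A reader could build that interval from the planned difference and standard error. But the standard error comes from a model that also contains the intravenous session, so residual variability after an intravenous dose feeds into the precision of a comparison between two patches. The two routes are also sampled differently: the Protocol Summary gives "60 min pre-IV administration and then up to 36 hr (1.5 days) post start of IV administration", against up to 192 hours for each patch. The documents do not show that the residual variances are equal.

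**Working it through.** **Inputs from the documents.** There are 24 completers, with dropouts replaced (section 5), allocated 12:12 to two sequences (section 4). The model has treatment, Session and sequence fixed and Subject within sequence random (section 8.3). The sample size is given without power, CV, expected ratio or margin, so there is no planned figure to reproduce.

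**Assumptions.** The within-subject CVs and the 80-125% limits are ours; the documents give neither.

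**1. What the missing interval would show.** For Sessions II-III alone, the residual df are 24 − 2 = 22. With σ = √ln(1 + CV²), SE = σ × √(2/24), and the 90% CI is the observed ratio multiplied and divided by exp(1.717 × SE). At CV 30%: σ = √ln(1.09) = 0.2936, SE = 0.0847, factor = exp(0.1455) = 1.157.

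| CV | SE | 90% CI at observed ratio 1.00 |
|---|---|---|
| 20% | 0.0572 | 0.91-1.10 |
| 25% | 0.0711 | 0.885-1.13 |
| 30% | 0.0847 | 0.865-1.16 |
| 40% | 0.1112 | 0.83-1.21 |

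**2. What the difference test shows instead.** Test results are from the noncentral t on 22 df. Two one-sided tests (TOST) at 0.05 use limits of ±ln 1.25.

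| True ratio | CV | Difference test | TOST passes |
|---|---|---|---|
| 0.80 | 20% | non-significant in 4% | 5% |
| 0.80 | 25% | non-significant in 15% | 5% |
| 0.80 | 30% | non-significant in 29% | 5% |
| 0.80 | 40% | non-significant in 52% | 4% |
| 0.95 | 10% | significant in 40% | 100% |
| 0.95 | 15% | significant in 21% | 99% |

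A ratio of 0.80 lies on the assumed limit, so TOST passes at most 5% by construction.

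Single results can also point in opposite directions:

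- Observed ratio 0.90 at CV 15%: p = 0.023, yet the 90% CI is 0.836-0.969, inside the assumed range.
- Observed ratio 0.85 at CV 40%: p = 0.16, yet the 90% CI is 0.702-1.029, which extends below 0.80.

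**3. Effect of the three-session model.** The design matrix has 24 × 3 = 72 rows and rank 27, which leaves 45 residual df. The intravenous rows have zero weight in the Mylan-Duragesic contrast, so they do not move the estimate. They do enter the residual variance: 22 df come from the patch sessions and 23 from each subject's intravenous value against the mean of the two patch values. If the intravenous residual SD is k times the patch SD, the pooled variance relative to the patch variance averages [22 + 23 × (2/3)(k² + 0.5)]/45:

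- k = 0.5: (22 + 23 × 0.5)/45 = 33.5/45 = 0.744
- k = 1: (22 + 23)/45 = 1.000
- k = 2: (22 + 23 × 3)/45 = 91/45 = 2.022

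By simulation, a nominal 90% CI for the patch ratio then covers 84%, 90% and 98% respectively, and the 0.05 test has a true size of 9.0%, 5.0% and 0.7%. The values of k are hypothetical.

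**The case against.** The strongest reply is that this is a reporting gap. Section 8.3 already plans the log transformation, the adjusted differences and their standard errors; only exponentiation and an interval level are missing. Nothing in the plan says that a non-significant result would be read as bioequivalence. The stated aim is to explore, and the objective in the Protocol Summary does not mention bioequivalence. This stands, and it is why the point ranks low. It does not remove the point: exploration still needs an estimate with its uncertainty, and the plan's only stated inference answers another question.

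A second reply is that the limits, the TOST comparison and every CV are assumed, and that 90% is a choice, since the only interval level in the documents is 95%. That is right. The figures show how far the two questions can diverge; they do not predict this trial.

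A third reply is that section 8.2.1 names AUC0-t and Cmax for the patches but AUC0-∞ for the intravenous dose, so it is unclear whether intravenous values enter every model. Section 8.3 does say that all three sessions are analysed for these measures, so the text supports the concern. At equal variances, however, this part disappears.

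One further argument should not be used against the plan: that its treatment test mixes in the intravenous arm. That arm is always Session I, so treatment adjusted for Session has a single df (rank 27 with treatment, 26 without), and that df is the Mylan-Duragesic contrast.

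**Conclusion.** The concern holds. No section available states a Mylan/Duragesic ratio or confidence interval for AUC0-t or Cmax, and section 8.3 reads continuously on this point. The prespecified inference for the first-listed objective is a difference test, which cannot support or refute bioequivalence.

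The size depends on variability that the documents do not give. At an assumed CV of 20% or below, missing a true ratio of 0.80 is a negligible risk; at 30-40% it would happen in about a third to a half of trials. At CVs of 10-15% the error runs the other way, with a harmless 5% difference often declared significant. The distortion from the intravenous variance is real only if the residual variances differ.

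This should be fixed, at the low end of that grade, because the aim is exploratory and the remedy is cheap.

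**What to change.** In section 8.3, for AUC0-t and Cmax:

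- Report the exponentiated Mylan minus Duragesic least-squares mean difference with its 90% CI as the basis for the exploratory comparison, and label it descriptive.
- Take it from a short additional model of Sessions II-III with treatment, Session and sequence fixed and Subject within sequence random. Alternatively, keep the three-session model and allow a separate residual variance for the intravenous session.
- State that the treatment p-value is not evidence for or against bioequivalence.
- Align section 8.1, for example: bioequivalence will be explored by estimating Mylan/Duragesic ratios with 90% CIs.

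**Cost.** One short model and a few sentences, with no new data. With 24 completers the point estimate does not change. If the variances are in fact equal, moving from 45 to 22 df widens the log-scale interval by about 2% (1.717/1.679 = 1.023). A descriptive interval gives no yes/no answer.

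**Optional.** If a verdict is wanted, fix the limits before the data are seen and require both endpoints. Under the assumed 80-125% limits, with both true ratios 1.00 and equal CVs, at least one endpoint would fail in about 6%, 30%, 60% and 94% of trials at CV 20%, 25%, 30% and 40% if the endpoints are independent, or 5%, 24%, 50% and 89% at a correlation of 0.8. That is why the descriptive report is the main proposal.

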ABSOLUTE BIOAVAILABILITY/PHARMACOKINETIC AND RESIDUAL DRUG ANALYSIS OF DURAGESIC® TRANSDERMAL SYSTEM AND GENERIC FENTANYL TRANSDERMAL SYSTEM IN HEALTHY ADULTS

Short title: Fentanyl Patch Pharmacokinetics in Healthy Adults

U01 Principal Investigator:

[name] (contact), PhD, RPh

Medically Accountable Investigator:

[name], MS

Sponsor:

Food and Drug Administration

NCT02531971

Version 13.0

01 February 2018

STATEMENT OF COMPLIANCE

This study will be conducted in compliance with the protocol, International Conference on Harmonisation Good Clinical Practice E6 (ICH-GCP) and the applicable Food and Drug Administration and other Department of Health and Human Services regulatory requirements.

All key personnel (all individuals responsible for the design and conduct of this study) have completed Human Subjects Protection Training.

PROTOCOL SUMMARY

Title:	Absolute Bioavailability/Pharmacokinetic and Residual Drug Analysis of Duragesic® Transdermal System and Generic Fentanyl Transdermal System in Healthy Adults
Population:	Healthy, non-smoking adults age 18-45 years
Number of Sites:	Single site: University of Maryland School of Medicine/General Clinical Research Center (GCRC)
Study Duration:	Approximately up to 18 months
Subject Participation Duration:	Approximately 12-18 weeks including the screening Session
Description of Study Products:	Fentanyl citrate injection, Fentanyl Duragesic®, matrix type, Janssen Pharmaceuticals transdermal drug delivery system (TDDS); Mylan (fentanyl) matrix type, Mylan Pharmaceuticals TDDS; naltrexone hydrochloride oral tablets and naloxone hydrochloride injections
Objective:	To determine serum fentanyl levels after using reference (Duragesic®) and generic fentanyl (Mylan) TDDS, and comparing them to the serum levels of intravenous fentanyl citrate, in healthy adult subjects
Description of Study Design:	This will be a three treatment, open-label, randomized, crossover clinical study with a Run-In Study Session (Study Session I) of intravenous fentanyl citrate, followed by a transdermal administration of a single strength of the reference listed drug (RLD) Duragesic®, and a transdermal administration of a generic equivalent to the RLD, Mylan fentanyl TDDS. A total of 24 subjects will be enrolled to complete this study.
	A) Pharmacokinetic Determination of Strength
	The study will be a three treatment, open-label, randomized crossover study, with a Run-In Study

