5 STUDY ENROLLMENT AND WITHDRAWAL

Only adult Subjects who meet the inclusion/exclusion criteria will be eligible for enrollment into this study. Twenty-four Subjects will be recruited and at least 10 alternates will be screened, as needed, to ensure that any dropouts will be replaced until a total of 24 Subjects complete all study procedures. The study population selected for this study includes healthy non-smoking adult men and women ages 18 to 45, inclusive. The selection criteria are designed to exclude persons who might have medical conditions that could pose a safety risk and persons whose medical conditions might interfere with the objectives and results of the study.

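### Absolute bioavailability is planned as a point estimate without an interval or individual values, and the stated mixed model cannot supply the patch–IV contrast

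*Combined protocol and SAP*

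**What the plan says.** The title opens "ABSOLUTE BIOAVAILABILITY/PHARMACOKINETIC AND RESIDUAL DRUG ANALYSIS OF DURAGESIC", and the first objective in section 3.1 includes the aim to "compare bioavailability to direct IV infusion of fentanyl citrate". Section 4 justifies opening with IV in every subject partly by the accuracy this brings to absolute bioavailability. The Protocol Summary and section 4 both state: "Each Subject will be his/her own control".

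Section 8.2.1 names AUC0-t and Cmax of the two patches as what "will be used as the primary endpoint". AUC0-∞ is to be determined for IV and for both patches.

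Section 8.3 fits a linear mixed model to log AUC and log Cmax from all three Sessions. Treatment, Session and sequence are fixed, and "The Subject within sequence will be treated as a random effect". It asks for least-squares mean differences between treatments and their standard errors. For F, it says that geometric mean AUCs "will be obtained by exponentiating the log transformed" AUC, "for all the three treatments to determine the absolute bioavailability". The AUC subscripts are garbled in the extracted text; I read them as AUC0-∞. A separate sentence says that F for both patches will be calculated. The text gives no formula for F, no per-subject F, no analysis set and no interval. The only confidence interval named anywhere in the supplied text is for release rates, at the end of section 8.

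On dropouts, section 5 says that "any dropouts will be replaced until a total of 24 Subjects complete all study procedures", and at least 10 alternates are to be screened.

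**The concern.** Every subject who completes the study supplies an IV profile and two patch profiles, so F can be formed within subject and its uncertainty taken from the spread of individual values. Section 8.3 instead stops at three treatment-level means. A reader of the report would see one F per product, with no statement of how well it is known and no view of how much it varies between people.

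The standard errors that 8.3 does request look like a way out, so it matters whether the stated model can produce one for patch minus IV. It also matters which subjects feed each mean. Everyone starts with IV, so a subject who leaves after Session I leaves an IV profile with no patch profile to match it.

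**Working it through.** The plan gives no power calculation, variance or margin for F, so it has no figure of its own to reproduce. I made four checks.

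**1. Does pairing change the point estimate?** For the same n subjects, the log of the ratio of geometric means is mean(log AUC patch) − mean(log AUC IV) = mean(log AUC patch − log AUC IV). The last term is the log of the geometric mean of individual ratios. The two are identical; a simulated set of 24 gave 7.6987 both ways. A dose factor common to all subjects multiplies both equally. Among 24 completers, F does not move.

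**2. Can the model in 8.3 give patch minus IV?** Inputs are the design table in section 4 and the fixed effects in 8.3. Write each cell mean as μ + treatment (τ) + Session (π) + sequence. The treatment and Session parts are:

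| | Session I | Session II | Session III |
|---|---|---|---|
| Arm 1 | τ(IV) + π1 | τ(D) + π2 | τ(M) + π3 |
| Arm 2 | τ(IV) + π1 | τ(M) + π2 | τ(D) + π3 |

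τ(IV) and π1 occur only together. Adding any constant c to π1 and subtracting it from τ(IV) leaves every cell mean unchanged, yet changes τ(D) − τ(IV) by c. No data can fix that contrast. In matrix form the columns number 1 + 2 + 2 + 1 = 6 (intercept, treatment, Session, sequence). For 24 subjects × 3 Sessions the rank is 5. Duragesic − IV and Mylan − IV are not estimable, nor is an IV least-squares mean averaged over Sessions. Duragesic − Mylan is estimable. If the model were instead fitted to Sessions II and III only, IV would not be in it and it would again say nothing about F.

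**3. What precision would a paired analysis give?** With n = 24, s = √ln(1 + CV²) and t(0.975, 23) = 2.069, the log half-width is 2.069 × s × √(2/24). The documents give no CVs, so these are assumptions:

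- CV 15%: s = 0.149; half-width 2.069 × 0.149 × 0.289 = 0.089; 95% CI ×/÷ 1.09.
- CV 30%: s = 0.294; half-width 2.069 × 0.294 × 0.289 = 0.175; 95% CI ×/÷ 1.19.

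The formula takes equal within-subject variance for IV and patch, and an F that does not itself differ between subjects. If F varies between subjects, the interval widens, and the paired analysis would show this.

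**4. What if IV-only dropouts enter the IV mean?** Suppose k such subjects have an IV AUC r times that of completers (k and r assumed). With raw means, log F shifts by −k/(24 + k) × ln r.

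| k | r = 1.25 | r = 1.5 |
|---|---|---|
| 1 | −0.9% | −1.6% |
| 3 | −2.4% | −4.4% |
| 6 | −4.4% | −7.8% |
| 10 | −6.4% | −11.2% |

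For example, k = 3 and r = 1.25 gives −(3/27) × 0.223 = −0.025, or −2.4%. A random-subject model with treatment means and no Session term shrinks these shifts, to between −0.5% and −2.8% for k = 3 and between −1.4% and −7.3% for k = 10. That range is over three assumed within-/between-subject CV pairs: 25%/50%, 25%/30% and 40%/30%. If r is below 1, the sign reverses. With a completers-only set the shift is zero.

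**The case against.** The best defence is that the analysis is not a set of unlinked means. The model has a random subject effect, gives log-scale treatment differences with standard errors, and 8.3 already derives patch parameters subject by subject. An exponentiated model difference would then be a within-subject F with an interval ready to hand. This would hold for a model without Session, or for a design with IV in more than one Session. It fails for the model as written, by check 2.

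Other parts of the defence stand:

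- A reader might infer that F is biased because it is not formed within subject. It is not: with 24 completers the estimate is the same.
- A reader might infer that the replacement rule itself mixes subjects. It does the opposite, by securing 24 people with all three Sessions. Mixing needs a further step, including the IV-only profiles, which no section states. A dropout may also leave before IV dosing or after wearing a patch, or there may be none.
- A reader might compare the paired interval with a wider one that treats the IV and patch means as independent. Nobody planned that analysis, so the comparison says nothing about this plan.
- F is not the headline result. The primary endpoint is patch AUC0-t and Cmax.

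Section 7 is absent from the supplied text, so a rule on analysis sets there cannot be ruled out.

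**Conclusion.** The point holds in a limited form. A title quantity, for which the IV run-in was partly designed, has no planned interval and no individual values, and the stated model cannot produce the patch–IV contrast or its standard error. That last result follows from the design alone and needs no assumption.

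The loss is one of precision and description; the point estimate among completers is unaffected. A paired 95% CI of about ×/÷ 1.09 to 1.19 is what the trial could report if within-subject CV is 15–30%.

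The dropout effect is conditional on IV-only profiles being used, and on assumed counts and AUC ratios. If leaving is unrelated to clearance, it adds random error but no bias. The k = 10 row is an outer illustration: it would need ten subjects lost after IV and before any patch, and section 5 gives only a minimum number of alternates to screen, with no expected dropout rate.

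The change is worth making before analysis, because it gives F an interval that the current text cannot deliver.

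**What to change.** Replace the geometric-mean sentence in section 8.3 with text to this effect: for each subject with an evaluable IV Session and an evaluable Session of the patch concerned, compute log F from that subject's own AUC0-∞ values, using the dose terms the sponsor already uses. For each product, report the geometric mean F with a paired 95% CI and list the individual values. Subjects with IV data only contribute to the description of IV pharmacokinetics and do not enter F.

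Add one sentence to the report stating that IV is confounded with Session I. The per-subject ratio does not remove this; it only avoids a Session term that the data cannot separate from IV. The mixed model can stay for Duragesic against Mylan, which it can estimate.

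The cost is a short change to the SAP text and one table. The downside is that IV profiles of subjects without a patch Session do not contribute to F. This point leaves the choice of dose terms untouched.

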6 STUDY PRODUCT

6.1 Study Product Description

6.1.1 Duragesic® (fentanyl) TDDS 25 µg/h

Duragesic® is a prescription TDDS that contains fentanyl which is a federally controlled substance (CII). Duragesic® TDDSs deliver fentanyl at a rate of 25 µg/h and are only for patients with chronic (around the clock) pain that is moderate to severe and expected to last for weeks or longer.

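### The Section 8.3 absorption rate relies on a steady-state concentration that a single 72 h wear would not reach on the plan's own 24 h half-life; an AUC-based rate avoids the problem

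*Combined protocol and SAP*

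**What the plan says.** Section 8.3 (Final Analysis Plan), on both patches: "steady concentrations (C_{ss}) of fentanyl in each Subject will be elucidated". It continues: "The rate of fentanyl absorption in each Subject is calculated by dividing the C_{ss} by the clearance predicted from the IV bolus data". The section gives no definition of Css, no time window, no check that a plateau was reached and no correction for incomplete accumulation.

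Section 4 (Study Design) supplies the only kinetic constant: "The half-life of fentanyl is approximately 24 hours". It uses this to justify the washout, on the ground that "5 days (i.e. 5 half-lives) will be sufficient for >95% of fentanyl to be eliminated from the body". It does not say whether 24 h describes disposition after IV dosing or the apparent decline after patch removal.

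In the Protocol Summary each patch is "to be worn for 3 days (72h"), and Section 4 describes one application per session. The same summary sets blood sampling to 36 h after the IV dose and to 192 h after patch application. Section 6.1.1 states that "Duragesic® TDDSs deliver fentanyl at a rate of 25 µg/h", and Section 6.1.2 gives the same nominal rate for the Mylan product. Section 8.2.1 already plans AUC0-infinity for the IV dose and for both patches.

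**The concern.** A steady-state concentration can be read off only if input has continued long enough for concentrations to level out. On the half-life in Section 4, 72 h is too short, so an observed plateau or late average lies below the steady-state value for that input rate.

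This is separate from the inverted formula in the same sentence. Css divided by CL does not have the units of a rate, whereas Css × CL does. Correcting the formula restores the units and leaves the accumulation shortfall in place. The result would then look plausible, which makes the remaining error harder to notice.

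The study estimates delivery in two ways, from serum concentrations and from residual drug, and its background says it should help inform guidance on characterising release and absorption. A serum-based rate that is too low by construction could be misread as a real disagreement between the two methods, or as under-delivery against the nominal 25 µg/h.

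**Working it through.** **Inputs.** Half-life 24 h (Section 4), so k = ln 2 / 24 = 0.0289 per h. Wear 72 h, IV sampling to 36 h and patch sampling to 192 h (Protocol Summary). Nominal input 25 µg/h (Sections 6.1.1 and 6.1.2). Assumptions for the base case: one compartment, constant input, CL known without bias.

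**Step 1: the plan's own figure.** Fraction eliminated after five half-lives = 1 − 2^(−5) = 96.9%. This agrees with the stated figure of more than 95%.

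**Step 2: approach to steady state.** The same expression, 1 − 2^(−t/24), gives the fraction of steady state reached under constant input. The mean over a window a to b is 1 − (e^(−ka) − e^(−kb)) / (k(b − a)). Multiplying by 25 µg/h gives the rate that Css × CL would report.

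| Value taken as Css | Share of true Css | Reported rate (µg/h) |
|---|---|---|
| 24 h | 50% | 12.5 |
| 48 h | 75% | 18.75 |
| 72 h (removal) | 87.5% | 21.9 |
| Mean 48-72 h | 82.0% | 20.5 |
| Mean 24-72 h | 72.9% | 18.2 |

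Reaching 95% of steady state takes 24 × log2(20) = 103.7 h. For 72 h to be enough, the half-life would have to be 72 / log2(20) = 16.7 h or less.

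**Step 3: only part of the disposition in the 24 h phase.** If a share f of the approach to steady state follows the 24 h phase and the rest is fast, the 72 h value is 1 − 0.125f. The documents give no f. For an assumed 0.3 to 0.8, the 72 h value is 96% to 90% of steady state, a shortfall of about 4% to 10%. The 24-72 h mean is 92% to 78%.

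**Step 4: declining release.** Let release fall during wear with a half-life of 24 to 144 h (assumed), keeping its mean at 25 µg/h. In one compartment the highest C × CL at any time is then 20.0 to 21.9 µg/h. Adding an assumed 2 h fast phase (f from 0.3 to 1), the 72 h value and both window means stay below 25 µg/h. The maximum alone can exceed it, when f is 0.5 or less and release is strongly front-loaded. The answer therefore depends on which value is called Css.

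**Step 5: the AUC-based alternative.** CL × AUC0-infinity / 72 h returns 25 µg/h exactly in the base case, with no steady state needed. The share of patch AUC beyond 192 h is 0.875 × 2^(−5) / k / 72 = 1.3%.

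**Step 6: what CL contributes.** IV sampling to 36 h covers 1 − 2^(−1.5) = 64.6% of IV AUC0-infinity in one compartment. A CL taken from the truncated AUC would be 1 / 0.646 = 1.55 times too high. The 72 h Css × CL product would then be 0.875 × 1.547 = 1.35 times the true rate, so the sign would reverse.

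**The case against.** The strongest reply concerns what the 24 h means. It appears only as a washout justification. Patch sampling runs 120 h past removal while IV sampling stops at 36 h, which is compatible with 24 h being an apparent post-patch half-life, though it does not prove it. If 24 h reflects slow uptake from the skin, C × CL tracks entry into blood, and that is the quantity Section 8.3 names. The gap would then lie between patch release and systemic absorption and would not be an error in the absorption rate. This stands, and it makes the finding conditional. It also means that a skin lag cannot simply be counted as making the bias worse.

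Second, the sign depends on CL. A reader might infer that the corrected rate is certain to be too low. The documents do not support that: Step 6 shows a truncated CL reversing the direction. Section 8.2.1 does specify IV AUC0-infinity, so this is an extrapolation risk and not an established error.

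Third, a reader might infer that the problem enters the t-test on release rates that closes Section 8.3. Nothing there shows that Css feeds it. The section describes cumulative release from residual drug and then says the release rate will be determined, without linking that rate to Css.

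Fourth, a common proportional bias largely cancels in the Duragesic/Mylan ratio if the time profiles match. The documents hold no onset data to say whether they do. It does not cancel against the residual-drug estimate or the nominal rate.

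Finally, Section 7 is not in the text reviewed, so a definition of Css there cannot be excluded. A defined window would not lift the 87.5% limit on an observed value under the base assumptions. A model-fitted Css would not be subject to that limit.

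**Conclusion.** The concern holds conditionally. If 24 h is the disposition half-life, input is roughly constant and CL is unbiased, Css × CL understates the absorption rate by 12.5% at removal, about 18% for a 48-72 h mean and about 27% for a 24-72 h mean. With an assumed 30-80% of the disposition in the 24 h phase, the shortfall at 72 h is about 4-10%. An unqualified claim of low bias would go beyond the documents, because they establish neither the nature of the 24 h figure nor the accuracy of CL.

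The quantity affected is the serum-based absorption rate and its comparison with residual drug and the nominal rate. The primary endpoints, AUC0-t and Cmax, do not use Css. The change should be made, because the rule as written needs a condition that the design does not secure and the inputs for a better rule are already planned.

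**What to change.** Replace the Css rule in Section 8.3 with, for each subject and product, mean absorption rate = CL(IV) × AUC0-infinity(TDDS) / actual wear time. This also removes the inverted formula. Note in the text that the numerator is the total amount absorbed, including any absorbed after removal, expressed per hour of wear.

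Deconvolution against the subject's own IV response may be added if the rate over time is wanted. Any average concentration during wear should be descriptive only, with its window fixed in advance.

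State that CL comes from the extrapolated IV AUC0-infinity or the compartmental fit, and not from the AUC truncated at 36 h. Report the extrapolated fraction of the IV AUC for each subject, with a sensitivity analysis of the absorption rate to that extrapolation.

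The cost is SAP wording and additional analysis, with no new data. The patch tail beyond 192 h is minor at about 1.3% of AUC. The larger limitation is that about 35% of the IV AUC is extrapolated on a one-compartment 24 h half-life. The replacement and the deconvolution both inherit that uncertainty, as Css × CL does, and the plan should say so.
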